### *Objective 3:*

To allow comparison of immunogenicity of surgical population to healthy non-surgical subjects, ~30 samples from B3451015 study (USA-only) and ~34 samples from B3451003 study (Japan only) will be included for OPA and cLIA testing of the four antigens.

For B3451015 which involved subjects aged 18 to <65 years, we will select the oldest available subjects with adequate serology sample remaining. For B3451003 study, we will select vaccinated subjects aged 65 to <86 years with adequate serology sample remaining.

Summaries of serological results will be generated comparing CP5/8, ClfA, and MntC GMTs between the following two groups: 1) Vaccinated surgical subjects without *S. aureus* infection from day of surgery before surgery (V2 admission) and 2) Vaccinated healthy subjects pooled from B3451015 and B3451003 at day 15 [visit window day 15 to 17].

As STRIVE surgical subjects' specimens range from 10 to 60 days after vaccination, comparison with healthy subjects will be limited to STRIVE subjects with specimens from Day 13 to Day 17 among the vaccinated controls selected for objective 1

We will perform ANCOVA controlling for demographics (age, sex, race, ethnicity, BMI), health status (diabetes, smoking status), days after vaccination, and country for this analysis. Additional secondary analysis for objective 3 will include comparison of healthy subjects with surgical subjects with *S. aureus* infection.

Least-squares means (LSMs) and associated CIs for both surgical and health non-surgical groups at their respective Day 15 visit window will be estimated from an ANCOVA. The dependent variable will be postvaccination titer at Day 15. The model terms will be country, demographics (age, sex, race, ethnicity, BMI), diabetes, smoking status and elapsed number of days after vaccination. Type 3 sums of squares will be used. Postvaccination titer at Day 15 will be log transformed. The difference between surgical and non-surgical groups in LSMs will be obtained for postvaccination visit Day 15. The exponentiated differences will be ratios of the surgical versus non-surgical groups' geometric means. The corresponding 2-sided 95% CIs will also be obtained.

*Objective 4:*

To compare the functional immune response of CP5/8, ClfA, and MntC at unscheduled BSI/SSI visit among vaccinated subjects with *S. aureus* infection with scheduled visits among vaccinated subjects without *S. aureus* infection, blood samples for immunogenicity will be collected at unscheduled visits for BSI/SSI assessment. Any subject with more than 1 unscheduled titer within a specified window will be summarized by the maximum titer.

An exponential decay curve estimating functional immune responses by days since vaccination of vaccinated STRIVE subjects at scheduled V2 hospital discharge visit not associated with *S. aureus* infection will be generated from among the 357 controls from objective 1 for comparison to vaccinated subjects with unscheduled BSI/SSI visits. Graphs of this decay curve will be generated and individual titers for vaccinated cases will be plotted at the appropriate days since vaccination.

ANOVA will be performed to compare serological results of functional antibody levels between the following 2 groups: 1) Unscheduled BSI/SSI visits among vaccinated subjects with *S. aureus* infection and 2) Scheduled V2 discharge visits of vaccinated subjects without *S. aureus* infection. The GMT ratio between cases and non-cases will be estimated, correcting for days since vaccination.

**Table 12. Sample Table – Total ~1450 Specimens**

Objective #	Sampling Plan	Number of Subjects	Number of Specimens
1-2	All 50 cases (+ 12 other SA infection) and 5 vaccinated controls & 2 unvaccinated controls per case	50 cases (+12 other) and 357 controls (Total 413)	50 x 5 time points = 250 12 x 5 time points = 60 350 x 3 time points = 1050 ~50 x 1 baseline = ~50 = 1410 specimens
3	SA4Ag vaccinated subjects without SA infection (from study above) and healthy non-surgical subjects from 1015 (US) and 1003 (Japan)	Additional 30 healthy vx controls (B3451015) and 34 healthy vx (B3451003)	Additional 64 specimens to above x 1 time point (15d) = 64 add'l specimens

**Table 13. Sample Table by Time Point for Serological Testing (n=~1450)**

Time points for testing	62 STRIVE case subjects	350 STRIVE control subjects	30 subjects from B3451015	34 subjects from B3451003
V1 Baseline	62	~50*		
V2 Admission	62	350		
V2 Discharge	62	350		
V5 (Day 90)	62	350		
All unplanned BSI/SSI visits	~30	~20		
Day 15 only from B3451015/B3451003			30	34
Total number of specimens	~278	~1120	30	34

\* 50 selected vaccinated controls will get V1 testing.

Statistical analyses for immunogenicity are summarized in [Section 8.2.3.5](#).

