### **8.1.3.5. Immunogenicity**

On December 20, 2018, the STRIVE study met its pre-specified futility criteria at its Interim Analysis and ceased enrollment. The rationale for this change in immunogenicity testing and analysis is to focus efforts on improving our understanding of why the vaccine did not appear to prevent post-operative *S. aureus* infections. This analysis will replace all previously planned immunogenicity analyses.

The immunogenicity testing and analysis will focus on the four objectives listed below:

Primary objective:

1. To assess the association between CP5/8, ClfA, and MntC functional antibody levels and *S. aureus* infections among subjects within the STRIVE study, adjusting for demographics, health status, and surgical characteristics

Secondary objective:

2. To describe the CP5/8, ClfA, and MntC functional antibody levels among surgical subjects at selected time points by case and vaccination status

Exploratory objectives:

3. To compare the functional immune response to CP5/8, ClfA, and MntC among vaccinated surgical subjects without *S. aureus* infection with vaccinated healthy (non-surgical) subjects
4. To compare the functional immune response of CP5/8, ClfA, and MntC at unscheduled BSI/SSI visit among subjects with *S. aureus* infection with scheduled visits of similar time intervals among subjects without *S. aureus* infection

Study Design:

A nested case-control study within the STRIVE study will be conducted to assess the association of *S. aureus* infection and immunogenicity endpoints at select timepoints, adjusting for demographics, health status, and surgical characteristics. Cases and controls will be matched by study site.

Cases will be any subjects (per protocol or mITT) with adjudication-confirmed *S. aureus*-related SSI and/or BSI (includes deep, organ/space and superficial SSIs). Infections with positive *S. aureus* cultures deemed not clinically significant by adjudicators will be excluded. Other invasive *S. aureus* infections will have descriptive analysis separate from objective 1 and without matched controls. At this time, there are 5 such cases: additional cases may be identified prior to study closeout.

Controls will be per protocol subjects from same study site as cases who completed Visit 5 (post-op Day 90) but did not develop adjudication-confirmed *S. aureus* infections. A total of 7 controls will be selected per case (5 vaccinated and 2 unvaccinated controls per case).

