At this time, the plan is to include a total of 51 cases of *S. aureus* infection (both SA4Ag vaccinated and placebo) and 357 controls will be included in this sub-analysis. For the few sites with a shortfall in available controls due to low enrollment, remaining controls will be randomly selected from other “case” sites (ie, sites with cases that have unselected controls remaining) to meet control targets. Extra controls will be associated with their actual site in the logistic regression analysis.

Data analysis:

All analyses will be performed for CP5/OPA, CP8/OPA, ClfA/cLIA, and MntC/cLIA.

*Objective 1:*

The key independent variables of interest are CP5 and CP8 functional antibody levels (as measured by OPA assay), and secondary independent variables include ClfA and MntC antibody levels (as measured by cLIA assay) assessed at the following time points.

The primary analysis will include the following immunogenicity variables (one value for each antigen for each specimen):

- Day of index surgery before surgery (V2 admission) log transformed titers
- V2 hospital discharge log transformed titers minus V2 admission log transformed titers [Quantify change from V2 admission]
- V5 post-op day 90 log transformed titers minus V2 hospital discharge log transformed titers [Quantify change from V2 discharge]

Multivariate conditional logistic regression will be conducted to model the odds of *S. aureus* infection based on functional antibody levels (ie, 3 immunogenicity variables based on V2 and V5 described above), adjusting for following covariates:

- Demographics (age, sex, race/ethnicity, BMI, ASA, CCI)
- Operative time (mins)
- Number of motion segments/intervertebral levels fused
- Proportion of blood loss (%)
- Units of transfusion
- Days from vaccination to surgery
- Days from surgery to discharge
- Primary versus revision spinal fusion surgery
- Season/year of surgery
- Colonization status (IHMA swab results)
- Diabetes
- Smoking status
- Intrawound antibiotic use (eg, vancomycin vs. other vs. none)

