#### *Objective 2:*

Tabular summaries and graphical displays of serological results by case/control status and vaccination status at each sampling time point will be generated. The immunogenicity baseline will be the Visit 1 prevaccination blood draw. Assay values from sera obtained up to 7 days before vaccination will be considered eligible for analysis.

The number and proportion of subjects achieving threshold values will be obtained at each scheduled time point for vaccine group. Threshold values are identified in [Table 8](#). Two-sided 95% CIs will be compiled. Comparisons will be conducted by vaccination and case status (ie, placebo-case, placebo-noncase, SA4Ag-case, and SA4Ag-noncase) using the Fisher exact test, 2-sided.

Vaccine groups will be summarized by proportion of subjects achieving each of 4 thresholds simultaneously. The 4 antigens will be CP5/OPA, CP8/OPA, ClfA/cLIA, and MntC/cLIA. These proportions will be compiled for each scheduled visit. Two-sided 95% CIs will be compiled for each proportion. The vaccine groups will be compared using the Fisher exact test, 2-sided.

GMTs at select time points (V1, V2, V2 discharge, V5, and unscheduled BSI/SSI visits) are obtained by log transformations of indicated values, averaging the log values, then exponentiating the result. The associated 2-sided 95% CI will be obtained by calculating the CI in log scale, referencing the t-distribution, and then exponentiating the lower and upper limits.

GMFRs are geometric means of the titer from the indicated visit divided by the corresponding baseline titer. Subjects missing either baseline or the applicable visit titer are excluded from the calculation. GMTs, GMFRs, and their 2-sided 95% CIs will be calculated for each scheduled time point.

GMTs, GMFRs, and their associated 2-sided 95% CIs will be calculated again for each select time point, but the statistics will be obtained for vaccine group and case occurrence (yes/no), ie, placebo-case, placebo-noncase, SA4Ag-case, and SA4Ag-noncase. These time profiles will be compiled for BSI cases, SSI cases, and ISA cases. Subjects who have more than 1 type of case will appear in as many case categories as relevant. Profiles will be calculated for all time points up to 90 days. Titers obtained after case onset will be excluded, so sample sizes for cases will shrink over time.

GMTs and GMFRs will also be obtained for the following subjects with unscheduled BSI/SSI visits:

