- Subjects with any postoperative *S aureus* BSI and/or deep incisional or organ/space SSI occurring within 90 days of the index surgery, limited to unscheduled blood draws within 90 days
- Subjects with any postoperative *S aureus* BSI and/or deep incisional or organ/space SSI occurring within 180 days of the index surgery, limited to unscheduled blood draws within 180 days
- Subjects with any postoperative *S aureus* SSI within 90 days of the index surgery, limited to unscheduled blood draws within 90 days
- Subjects with any postoperative *S aureus* SSI within 180 days of the index surgery, limited to unscheduled blood draws within 180 days
- Subjects with any adjudicated postoperative ISA disease within 90 days of the index surgery, limited to unscheduled blood draws within 90 days
- Subjects with any adjudicated postoperative ISA disease within 180 days of the index surgery, limited to unscheduled blood draws within 180 days

Subjects with more than 1 endpoint of unplanned BSI/SSI assessment will participate in each relevant analysis.

If a specific unscheduled assessment visit was not done, serology samples collected at scheduled visits occurring within 7 days before or after the onset of a PDI may be used in these analyses.

Two additional analyses using ANCOVA will be performed to assess the association between absolute functional antibody levels (at V1 versus V2, V2 versus V2 discharge) and possible interfering host factors, include interaction terms.

1) *ANCOVA comparing V1 versus V2 admission*: This sub-analysis will be limited to those with serological testing at V1 which includes 51 cases and a subset of ~50 controls (chosen from among the 2 vaccinated controls per vaccinated case matched by site). Least-squares means (LSMs) and associated CIs for both vaccine groups at each postbaseline visit will be estimated from an analysis of covariance (ANCOVA). The dependent variable will be log V2 admission titer minus log day-of-vaccination (V1) titer. The model terms will be vaccine group, site, demographics (age, sex, race/ethnicity, BMI, ASA, CCI), colonization status at V1, diabetes, smoking status and elapsed number of days from V1 to V2 admission. Colonization status will be based on any *S aureus* at V1 and will be defined as positive if either nose or throat is positive; otherwise, it will be defined as negative.

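### No placebo control gets a Visit 1 titer, so placebo-noncase fold rises cannot be computed and the V1-V2 ANCOVA sets an all-case placebo group against a mixed SA4Ag group

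*SAP*

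**What the plan says.** After the trial met its futility criterion, SAP Section 8.1.3.5 replaced all planned immunogenicity analyses with a nested case-control study. It takes "a total of 51 cases of *S. aureus* infection (both SA4Ag vaccinated and placebo) and 357 controls", with "5 vaccinated and 2 unvaccinated controls per case". Unvaccinated must mean placebo, since controls are per-protocol subjects.

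Three places settle who has a baseline titer. For the ANCOVA of Visit 1 (V1) against Visit 2 (V2) admission, Objective 2 states: "This sub-analysis will be limited to those with serological testing at V1 which includes 51 cases and a subset of ~50 controls". These controls are "chosen from among the 2 vaccinated controls per vaccinated case matched by site". Table 12 budgets "50 x 1 baseline = ~50" for controls. The Table 13 footnote reads: "50 selected vaccinated controls will get V1 testing".

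The same section and Table 26 plan four kinds of output that depend on V1:

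- GMFRs in four groups, "ie, placebo-case, placebo-noncase, SA4Ag-case, and SA4Ag-noncase". Subjects lacking a baseline or visit titer are left out.
- Fisher exact comparisons of threshold attainment across the same four groups. Table 8 defines the ClfA and MntC thresholds as at least a 4-fold rise from Visit 1; the CP5 and CP8 thresholds are absolute titers.
- Attainment of all four thresholds together, and 2- to 32-fold rises. Neither is split by case status.
- The V1-V2 admission ANCOVA: "The dependent variable will be log V2 admission titer minus log day-of-vaccination (V1) titer". Its terms are vaccine group, site, demographics, colonization, diabetes, smoking and elapsed days. The reported contrast is SA4Ag against placebo.

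Section 7 rules out imputing missing immunogenicity values.

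**The concern.** The sampling plan and the analysis plan do not match. Objective 2 names placebo noncases as a group to be summarized for fold rise, but the assay budget gives none of them a baseline.

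The ANCOVA has a related fault. It estimates a vaccine-group contrast in a sample where one arm was selected entirely on the outcome and the other only partly, with no term for the outcome. The section's stated aim is to understand why the vaccine did not appear to prevent infection. A fold-rise contrast in which vaccine group and case status are entangled is poorly suited to that aim.

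**Working it through.** **Reproducing the plan's specimen counts (Table 13).**

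- Cases: 62 subjects × 4 scheduled time points + 30 unplanned visits = 278. Stated: ~278.
- Controls: 50 at V1 + 350 × 3 + 20 unplanned visits = 1120. Stated: ~1120.
- Total: 278 + 1120 + 30 + 34 = 1462. Stated: ~1450.

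Table 12 agrees for Objectives 1 and 2: 50×5 + 12×5 + 350×3 + 50 = 1410, as stated. The totals leave room for about 50 control baselines, and the footnote assigns all of them to vaccinated controls. The SAP uses 51 cases with 357 controls in some places and 50 with 350 in others; this does not affect the point.

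**Placebo controls with a baseline.** Two per case gives 2 × 50 = 100 to 2 × 51 = 102 placebo controls. With a V1 titer: 0.

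**Consequences for each output.**

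- GMFR, placebo noncase: n = 0 at every visit, by the exclusion rule.
- ClfA and MntC thresholds, placebo noncase: n = 0, because the threshold is itself a rise from V1.
- All four thresholds together: Table 26 excludes subjects missing any assay, so every placebo control drops out and the placebo group is cases only.
- 2- to 32-fold rises: the placebo group is again cases only.

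**Composition of the V1-V2 ANCOVA.** The SAP does not give the split of cases by arm. Assume that ~50 means two controls per vaccinated case:

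| Control baselines | SA4Ag cases (÷2) | Placebo cases (51 − SA4Ag) | SA4Ag subjects in model | Placebo subjects in model |
|---|---|---|---|---|
| 45 | 22.5 | 28.5 | 67.5 | 28.5, all cases |
| 50 | 25 | 26 | 75 | 26, all cases |
| 55 | 27.5 | 23.5 | 82.5 | 23.5, all cases |

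One third of the SA4Ag subjects are cases in every row (for example 25/75), against all of the placebo subjects.

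**What the contrast then estimates.** Let d_S and d_P be the case-minus-noncase difference in mean log fold change within SA4Ag and within placebo. Ignoring covariates, the fitted contrast differs from the SA4Ag-placebo difference among noncases by (1/3)·d_S − d_P. The term d_S can be estimated from the planned assays. The term d_P cannot, because there are no placebo noncases with a baseline.

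**Comparison with the companion model.** The V2 admission-discharge ANCOVA in the same section includes case status and its interaction with vaccine group. The V1-V2 model has neither, in the text or in Table 26.

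**The case against.** The strongest reply is that little of importance depends on these cells. Objective 1 uses the V2 admission titer and later changes, and no V1 value. CP5 and CP8 are its key variables, and their thresholds are absolute. The contrast that speaks most directly to vaccine failure, SA4Ag cases against SA4Ag noncases, keeps its fold rises with about 50 noncases. The GMFRs are descriptive, the ANCOVAs are framed as a search for interfering host factors, and all immunogenicity endpoints are exploratory. All of this stands and limits the weight of the point.

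Two stronger readings are tempting, and the documents support neither:

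- A reader might infer that the noncase reference is missing for every fold-rise measure. Only placebo noncases are missing, and the n-fold rises and the all-four-antigen threshold have no planned placebo-noncase cell to be empty.
- A reader might infer that infection altered the titers in the ANCOVA. Its outcome ends at V2 admission, before surgery, so a postoperative infection cannot have changed it. The fault is selection on the outcome. It biases the contrast only if future cases and noncases already differ in pre-surgical fold change, and the documents give no figure for that.

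Two possible rescues fail. Section 6.3.5 mentions assays at randomization for selected uninfected subjects, but that general wording does not override the vaccinated-only rule in Objective 2 and Table 13. In profiles compiled separately for BSI, SSI and ISA, a placebo subject with one infection type might count as a noncase for another, but that subject is still infected.

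**Conclusion.** The point holds within limits. The placebo-noncase GMFRs and the placebo-noncase cells of the ClfA and MntC threshold comparisons cannot be computed: 0 of 100 to 102 placebo controls have a baseline. The placebo results for n-fold rises and for the all-four-antigen threshold would describe infection cases only.

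The V1-V2 admission ANCOVA compares a placebo group made up wholly of cases with an SA4Ag group that includes about 50 noncases, and does not adjust for case status. Its SA4Ag-placebo contrast is confounded with outcome-dependent sampling, by an amount that cannot be determined from the documents. The figures of about 75 against 26 subjects rest on the assumption about the case split; that all placebo subjects are cases does not.

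SA4Ag case versus noncase fold rises, GMTs after Visit 1, the absolute CP5 and CP8 thresholds, Objective 1 and the efficacy analyses are unaffected.

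**What to change.** Label: cheap improvement.

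1. Add case status to the V1-V2 admission ANCOVA, as the V2 admission-discharge ANCOVA already does. This costs nothing. With the present sampling only the main effect can be fitted, and the vaccine contrast then rests on SA4Ag cases against placebo cases under additivity.
2. Keep the ~50 vaccinated-control baselines and add V1 assays for about 50 site-matched placebo controls. Protocol Section 7.4 plans a prevaccination sample from every subject, and Section 7.5 allows remaining sera to be stored for up to 15 years. The Table 13 sum goes from 1462 to 1512 specimens (50/1462 = 3.4%); the downside is this assay cost. The empty cells are then filled, and the case status by vaccine group interaction can be fitted.

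Splitting the existing 50 into 25 and 25 would avoid new assays, but it would inflate the standard error of the SA4Ag-noncase GMFR by √(50/25) = 1.41 and weaken the most informative contrast. Adding assays is preferable.

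If no assays are added, withdraw the placebo-noncase fold-rise and ClfA/MntC threshold outputs, and label every placebo result that uses a V1 titer as cases only.

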**8.1.4. General Considerations**

Day of surgery will be labeled Day 1. The day prior will be Day -1. However, in the analyses of local reactions and systemic events, the 10 days after vaccination will be referred to as Days 1-10.

All CIs for proportions will be 2-sided 95% intervals, obtained using the exact Clopper-Pearson method, as described by Agresti.

Performance of the van Elteren test will use modified ridit scores (Stokes et al).

Based on FDA recommendations, subgroup analyses will be performed for efficacy and selected immunogenicity analyses. The proposed subgroups will be defined by the following:

- Race
- Age group (18 to <50, 50 to 64, and 65 to <86 years)
- Sex
- Ethnicity (Hispanic/Latino and not Hispanic/Latino)
- Smoking status (current smoker, past smoker, and never smoked)
- Site (sites may be combined by similar rates of SSIs following surgery)
- Type of surgeon (as defined in [Section 6.3.2](#))
- Country
- CCI score substituting for medical history; CCI levels will be 0, 1, 2, and  $\geq 3$
- Colonization status at the time of surgery
- Colonization status at the time of vaccination
- Timing of surgery after vaccination (1-14 days, 15-30 days, 31-45 days, 46-64 days, and 65 days or more after vaccination)

Analyses with limited numbers of cases per subgroup may not be performed.

Colonization status at the time of surgery is defined as follows:

- Positive for any subject with at least 1 positive *S aureus* colonization swab at 1 anatomical site or both anatomical sites on the day of surgery
- Negative for any subject with negative *S aureus* colonization swabs at both anatomical sites and not more than 1 missing colonization result on the day of surgery
- Missing for subjects without any colonization swab results from either anatomical site on the day of surgery

The definition of colonization status for “any anatomical site” is the same for colonization at the time of vaccination and colonization on the day of surgery:

- Positive for any subject with at least 1 positive *S aureus* colonization swab at either anatomical site or both anatomical sites
- Negative for any subject with negative *S aureus* colonization swabs at both anatomical sites and not more than 1 missing colonization result
- Missing for subjects without any colonization swab results from either anatomical site

All statistically significant results associated with subgroup analyses will be regarded as hypothesis generating.

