9.3.4.2. Colonization Analysis

Windows for obtaining colonization swabs will be the same as for immunogenicity. Colonization swabs at Visit 2 (index hospital admission) will be collected both on admission and again, prior to discharge.

Baseline colonization status is defined as:

- Positive for any subject with at least 1 positive *S aureus* colonization swab at either Visit 1 or Visit 2 (admission sample only) or both.
- Negative for any subject with all negative *S aureus* colonization swabs at both Visit 1 and Visit 2 (admission sample only) and no missing colonization swabs.
- Missing for subjects without any colonization swab results from either Visit 1 or Visit 2 (admission sample only) or subjects with any combination of negative colonization swabs and at least 1 missing colonization swab.

At each postsurgery time point, the proportions of colonization swabs testing positive for *S aureus* at each anatomical site and the RR between the 2 vaccine groups along with its exact 2-sided 95% CI will be obtained. Subgroup compilations will be performed based on

age group, sex, baseline colonization status, and primary endpoint status (ie, case or noncase). Statistical significance of treatment-subgroup interactions will be obtained from logistic regression. The logistic regression will include treatment, subgroup, and treatment-subgroup interaction. One subgroup will be examined at a time. Some subgroups may be combined to achieve reasonable sample size. Anatomical sites will be examined separately.

Analyses will be performed for the per-protocol and mITT populations, further limited to subjects having at least 1 nonmissing colonization swab value at any visit.

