Missing values will not be imputed for any immunogenicity, safety, demographic, or colonization variables. However, immunogenicity values less than LLOQ will be set as  $0.5 \times \text{LLOQ}$  for the analysis.

Subjects who are vaccinated but do not undergo the index surgery will not have a Day 1 visit. Their last day in the study will be labeled Day -1.

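### The SAP's colonization definitions let subjects with missing swabs count as noncarriers: explicitly in two titer models, and through self-contradictory wording in Section 8.1.4

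*SAP*

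**What the plan says.** Protocol Section 9.3.4.2 defines baseline colonization from the Visit 1 swabs and the Visit 2 admission swabs. Negative requires all of them to be negative "and no missing colonization swabs". Missing covers subjects with no results and also "subjects with any combination of negative colonization swabs and at least 1 missing colonization swab".

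SAP Section 8.1.4 defines status at the time of surgery and, separately, status for any anatomical site at vaccination or surgery. Negative requires negative swabs at both sites "and not more than 1 missing colonization result on the day of surgery"; the second definition has the same allowance, "not more than 1 missing colonization result", without naming the day. Missing is confined to subjects with nothing from either site: "Missing for subjects without any colonization swab results from either anatomical site on the day of surgery".

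SAP Section 6.3.1 takes baseline as Visit 1 and/or the Visit 2 admission sample and refers to Section 8.1.4 for combining sites. SAP Section 8.2.1 uses colonization at surgery (any *S aureus*, MRSA, MSSA) as efficacy subgroups 8 to 10.

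In SAP Section 8.1.3.5, Objective 2, both ANCOVA models (Visit 1 versus Visit 2 admission, and Visit 2 admission versus discharge) include colonization status, which "will be defined as positive if either nose or throat is positive; otherwise, it will be defined as negative".

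SAP Section 7 states: "Missing values will not be imputed for any immunogenicity, safety, demographic, or colonization variables".

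**The concern.** An absent swab carries no information on carriage. If such subjects are filed as negative, some carriers enter the noncarrier group. Efficacy by baseline colonization is a stated exploratory objective with its own rows in SAP Table 14, and colonization is an adjustment term in both titer models.

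Misclassification of this kind blurs the carrier/noncarrier contrast. Because VE is computed from the case split alone (SAP Section 8.1.1, VE = 1 - [p/(1 - p)], which equals 1 - x/y for x vaccine and y placebo cases), moving one case matters in a small stratum. In an invented stratum with 6 vaccine and 6 placebo cases, VE = 1 - 6/6 = 0%. Take out one placebo case and VE = 1 - 6/5 = -20%.

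The Section 8.1.4 wording raises a separate problem. Two programmers could build different subgroups from the same sentence.

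**Working it through.** **Step 1. Apply the rules to every swab pattern.** The plan states no figure to reproduce. With nose and throat each positive, negative or missing, one visit has 3 x 3 = 9 patterns.

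| Pattern at one visit | Number | 8.1.4, allowance given effect | 8.1.4, read literally | Protocol principle applied to one visit | ANCOVA rule |
|---|---|---|---|---|---|
| Any positive | 5 | Positive | Positive | Positive | Positive |
| Both negative | 1 | Negative | Negative | Negative | Negative |
| One negative, one missing | 2 | Negative | no category | Missing | Negative |
| Both missing | 1 | Missing | Missing | Missing | Negative |

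Section 8.1.4 is in doubt only for the third row. The ANCOVA rule differs from the protocol principle in the third and fourth rows.

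**Step 2. Baseline status over four swabs** (two sites, two visits). There are 3^4 = 81 patterns, of which 2^4 = 16 contain no positive. The protocol calls 1 of these Negative and 15 Missing. The ANCOVA wording, applied to Visit 1 or Visit 2 admission as in the second model, calls all 16 Negative. Section 8.1.4 gives no rule for combining the two visits, although Section 6.3.1 relies on it for baseline.

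**Step 3. Illustrate the size at one visit.** Inputs:
- Missing rate per swab, m: 1%, 5% or 10%, independent between swabs. This is an assumption; the documents give none.
- Carriage, c: 20% to 50%, from Protocol Section 1. That figure covers several body surfaces in people generally, so it is only a guide to nose and throat carriage here.
- Share of carriers positive at one site only, s: 70%. This is an assumption.

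Formulas, with Section 8.1.4 read so that negative plus missing is Negative:
- Carriers coded Negative: A = c x s x m(1 - m)
- Noncarriers coded Negative: B = (1 - c)(1 - m^2)
- Carrier share of the Negative group: A/(A + B)
- Share of the Negative group with a missing swab: [(1 - c) x 2m(1 - m) + A]/(A + B)
- ANCOVA rule on one visit: carriers A' = A + c x m^2, noncarriers B' = 1 - c, share A'/(A' + B')

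At the upper end (c = 0.5, m = 0.10):
- A = 0.5 x 0.7 x 0.09 = 0.0315 and B = 0.5 x 0.99 = 0.495.
- Carrier share = 0.0315/0.5265 = 6.0%.
- Share with a missing swab = (0.5 x 0.18 + 0.0315)/0.5265 = 23.1%.
- ANCOVA: A' = 0.0315 + 0.005 = 0.0365, share = 0.0365/0.5365 = 6.8%.

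| m | Carriers in 8.1.4 Negative group | Carriers in ANCOVA Negative group (one visit) | 8.1.4 Negative group with a missing swab |
|---|---|---|---|
| 1% | 0.2-0.7% | 0.2-0.7% | 2.1-2.7% |
| 5% | 0.8-3.2% | 0.9-3.5% | 10.3-12.4% |
| 10% | 1.6-6.0% | 1.8-6.8% | 19.5-23.1% |

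Each range runs from c = 20% to c = 50%. The first two result columns are shares of the Negative group, not shares of carriers. For the four-swab baseline variable, the chance of at least one missing swab is 1 - (1 - m)^4 = 3.9%, 18.5% and 34.4%.

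**The case against.** The best defence has four parts.

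**The SAP may depart from the protocol.** Protocol Section 9 lets the SAP modify plans, with an amendment needed only for major primary-endpoint changes. That stands, so the departure is not forbidden. But nothing in the SAP announces or explains it, and the SAP's change log for Amendment 3 says baseline colonization was defined for consistency with the protocol.

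**The protocol rule covers baseline status only.** This stands. A reader might infer that efficacy subgroups 8 to 10 breach the protocol. They do not, because the protocol defines no time-of-surgery variable; the fault there is the inconsistent wording. A reader might also infer that wholly unswabbed subjects enter those subgroups as negative. Section 8.1.4 explicitly keeps them Missing. Nor is it certain that one negative plus one missing is Negative: the literal text leaves that subject unclassified.

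**Section 7 could be taken to govern the ANCOVA models**, so that the catch-all negative applies only to subjects with results. That reading is possible, but the definition has no such limit and provides no Missing class. For Section 8.1.4 the no-imputation argument is weaker, since deriving a composite from the swabs in hand is not plainly imputation. The point does not rest on it there.

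**Little depends on this.** The primary and secondary efficacy analyses use no covariates (SAP Section 6.4), significant subgroup results are labelled hypothesis generating (Section 8.1.4), and the titer models were written after the futility stop (Section 8.1.3.5). This stands and keeps the point minor.

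**Conclusion.** The point holds as a minor error of definition. The two ANCOVA definitions, as written, turn missing colonization into negative, contrary to SAP Section 7 and to the protocol's baseline rule. Section 8.1.4 contradicts itself for subjects with one negative and one missing swab, and through Section 6.3.1 the baseline variable departs from the protocol's definition.

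The size cannot be determined from the documents and depends on the unknown missing-swab rate. Under the stated assumptions, carriers make up about 0.2-6.0% of the Section 8.1.4 Negative group and 0.2-6.8% under the one-visit ANCOVA rule. It is tempting to take the protocol's 20-50% carriage as the error rate. That figure is general multi-site colonization, and it could at most describe subjects whose swabs are missing, whose number is unknown. The effect is confined to exploratory colonization analyses, subgroups and titer models; the primary analysis is untouched.

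**What to change.** Reword four definitions: the two in SAP Section 8.1.4 and the two ANCOVA definitions in Section 8.1.3.5.
- Positive: any positive swab among those required for the variable.
- Negative: every required swab is available and negative. For single-visit status that means both sites at the visit; for baseline status, both sites at Visit 1 and at Visit 2 admission, as in Protocol Section 9.3.4.2.
- Missing: no positive swab and at least one required swab absent.

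In the titer models, treat Missing as a missing covariate: exclude those subjects, or give them their own level if numbers allow. The Visit 1 model has only 51 cases and about 50 controls, so a separate level may be nearly empty. Report Missing counts by arm, and keep the present coding as a sensitivity analysis if wanted.

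No new data are needed. The cost is smaller Negative groups: about 2-23% of the Section 8.1.4 Negative group would move to Missing under the assumptions above. The rule is also asymmetric, since a positive with a missing swab stays Positive while a negative with a missing swab is set aside. Apparent carriage among classified subjects therefore rises somewhat, which is a further reason to report the Missing counts.
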